6.2.2. Analysis Methods

Descriptive statistics (for example, may include n, mean, SD, minimum, median, and maximum) will be calculated for each laboratory analyte for observed values and changes from baseline at each scheduled time point by intervention arm and study phase.

Shift tables will be provided summarizing the shift in laboratory values from baseline over time with respect to abnormality criteria (low, normal, high) for each laboratory parameter by study phase.

The cross-tabulations of the worst toxicity grades over time versus baseline grade and the worst abnormalities versus baseline grade per parameter and per analysis phase will be presented including also the number of participants per worst grade and the number of participants per abnormality.

A tabulation of percentage and number of the participants who have treatment-emergent worst toxicity grades and treatment-emergent worst abnormalities per parameter, time point and per analysis phase will be included. The incidence table of worst toxicity grade abnormality in laboratory parameters will be also presented stratified by the subgroup of interests identified in Section 2.4.2.

Plots of mean (+/- SE) values and changes from baseline over time for selected laboratory parameters will be presented by intervention arm.

A listing including all parameters with at least one treatment-emergent toxicity or abnormality per participant (exclusion of urinalysis) will be generated.

Spaghetti-plots for selected laboratory parameters may be presented by intervention arm over time (with Week shown on x-axis).

6.2.3. Creatinine and Glomerular Filtration

Unless otherwise specified, time points to be evaluated for these creatinine and glomerular filtration analyses will be Baseline, Week 12, Week 24, Week 36 and Week 48.

6.2.3.1. eGFR

Stages of eGFR at baseline versus the minimum post-baseline eGFR value and the last available value will be summarized by count and percent of participants. Kidney disease stages are defined as follows: 1 (Normal): eGFR ≥ 90 ; 2 (Mild): eGFR 60-89; 3 (Moderate): eGFR 30-59; 4 (Severe): eGFR <30.

In addition to the above, the number and proportion of participants with a 10-<30%, 30-<50% and $\geq 50\%$ decrease from baseline will be tabulated.

Scatter plots of GFR versus other renal biomarkers (total urine protein, total urine albumin, urine protein to creatinine ratio [UPCR], urine albumin to creatinine ratio [UACR], retinol binding protein (RBP) and beta-2-microglobulin, RBP to creatinine ratio and beta-2-microglobulin to creatinine ratio, and urine fractional excretion of phosphate [FEPO4]) will also be presented.

6.2.3.2. Proximal Renal Tubular Function

Proteinuria by Quantitative Assessment

Total urine protein, total urine albumin, UPCR and UACR will be summarized by intervention arm and visit using descriptive statistics.

The number and proportion of participants with UACR and UPCR results in the following categories over time will be tabulated:

- UACR: < 30, \geq 30 to 300, >300 mg/g
- UPCR: < 200 mg/g versus \geq 200 mg/g

Median (Q1, Q3) percent change from baseline over time will be plotted by intervention arm.

The evolution over time of total urine protein and total urine albumin will also be presented.

Proteinuria by Urinalysis (Dipstick)

Treatment-emergent proteinuria by urinalysis (dipstick) over time will be summarized by intervention arm. Cross-tabulation of grades overtime versus baseline will also be presented.

Other Renal Biomarkers

Selected renal biomarkers RBP and beta-2-microglobulin, RBP to creatinine ratio and beta-2-microglobulin to creatinine ratio will be summarized by intervention arm and visit using descriptive statistics.

The proportions of participants with beta-2-microglobulin to creatinine ratio ≤ 343.5 $\mu\text{g/g}$ and > 343.5 $\mu\text{g/g}$ will be tabulated.

The number and proportion of participants with RBP to creatinine ratio results in the following categories overtime will be tabulated:

- < 50 years of age: < 130 mcg/g creatinine, \geq 130 mcg/g creatinine
- \geq 50 years of age: < 172 mcg/g creatinine, \geq 172 mcg/g creatinine

Phosphate excretion

Other renal biomarkers include FEPO4 that will be summarized by intervention arm and visit using descriptive statistics.

FEPO4 will be calculated as follows:

- Based on unadjusted serum creatinine:

$$\text{FEPO4 (\%)} = (\text{SCr} \times \text{UPO4}) / (\text{SPO4} \times \text{UCr}) \times 100 (\%)$$

Where SCr is serum creatinine concentration, UPO4 is urine phosphate concentration, SPO4 is serum phosphate concentration, and UCr is urine creatinine concentration.

The proportions of participants with FEPO4 $\leq 10\%$ and $> 10\%$ will be tabulated.

The baseline, post-baseline, and change from baseline in FEPO4 will be summarized by intervention arm and visit using descriptive statistics. Median (Q1, Q3) change from baseline in FEPO4 over time will be plotted by intervention arm.

Subclinical renal proximal tubulopathy

Potential Markers of Renal Proximal Tubulopathy are:

1. Confirmed increase in serum creatinine ≥ 0.40 mg/dL from baseline.
2. Confirmed ≥ 2 grade level increase from baseline in graded proteinuria
3. Confirmed ≥ 1 grade level increase from baseline in graded hypophosphatemia
4. Confirmed ≥ 1 grade level increase from baseline in graded glycosuria concurrent with serum glucose ≤ 100 mg/dL (normoglycemic glycosuria)

A confirmed laboratory abnormality is defined as an abnormality observed at 2 consecutive post-baseline measurements or an abnormality observed at 1 measurement followed by study drug discontinuation.

A subclinical renal proximal tubulopathy will be defined as confirmed abnormalities in any 2 out of the 4 renal parameters (serum creatinine and one or more of the 3 other markers of tubular dysfunction).

Baseline Subclinical renal proximal tubulopathy

Potential Markers of Renal Proximal Tubulopathy at Baseline:

1. Grade ≥ 1 serum creatinine
2. Grade ≥ 2 proteinuria
3. Grade ≥ 1 hypophosphatemia
4. Grade ≥ 1 glycosuria concurrent with serum glucose ≤ 100 mg/dL (normoglycemic glycosuria)

A baseline subclinical renal proximal tubulopathy will be defined as abnormalities in any 2 out of the 4 renal parameters (serum creatinine + 1 or more of the 3 other markers of tubular dysfunction).

6.3. Electrocardiogram

6.3.1. Definitions

Evaluation of the triplicate 12-lead ECGs will be based on the mean value of the triplicate parameters and the abnormalities will be defined on the triplicate means.

The following ECG parameters measurements will be analyzed:

- PR interval (ms)
- Heart Rate (bpm)
- QT interval (ms)
- QRS duration (ms)
- QTc Corrected (Fridericia's formula QTcF)

The abnormalities in ECG parameters will be determined according to the criteria specified in the Cardiovascular Safety – Abnormalities Table (see Clinical Protocol Appendix 6, Cardiovascular Safety- Abnormalities Table). Abnormalities on actual values are provided for HR, PR, QRS and QTcF. Additional abnormalities on change from baseline will be provided for QTcF. No abnormalities will be defined for actual uncorrected QT values. Uncorrected QT \geq 500 ms will be flagged and only shown in listings.

An assessment is treatment-emergent if /abnormality worsened as compared to the abnormality at baseline; this also includes the shift from abnormally high to abnormally low and vice-versa. Post-reference abnormalities are always treatment-emergent with regard to missing abnormalities at baseline. The abnormally high values (i.e. abnormally high, borderline prolonged, prolonged, pathologically prolonged) versus the abnormally low values are considered equally important. Abnormalities defined on changes from baseline are always treatment-emergent.

For each parameter, a “worst-case” analysis will be performed by using the worst abnormality and time point per participant. Worst-case will be derived within each phase, including unscheduled assessments. In case the same subject has both abnormalities (low and high) for the same test within the same phase, the participant will be counted in the analysis for both abnormality directions (abnormally high and low).

Change from baseline is defined as follows: value at a given time point minus baseline value.

6.3.2. Analysis Methods

Only data from the vendor ERT will be analyzed. All other ECG data will be listed.

For the time points on which triplicate ECGs apply, a rounded mean value to the next integer per triplet will be calculated per time point before any further handling. This rounded mean value will be used through the entire analysis also in case of 1 or 2 missing values.

ECG records with partial dates (any of day/month/year is missing) will not be used in analysis, except in the listings. The following imputation rules will be applied.

If heart rate (HR) is missing, it will be calculated using RR (if available) and rounded to the integer value (see formula below) before any further handling if applicable.

$$\frac{1000}{RR(ms)} = \frac{HR(bpm)}{60}$$

HR from the vital signs section (i.e. pulse) will not be used in this ECG analysis section. RR values (if available) will only be listed. Recalculated HR values will be flagged.

Descriptive statistics will be calculated for observed values and changes from baseline per parameter (all parameters except for RR) at each scheduled time point by intervention arm.

Shift tables will be provided summarizing the shift in ECG values from baseline over time with respect to abnormality criteria (low, normal, high) for each parameter by study phase.

A cross-tabulation of the worst abnormalities (on actual values) versus baseline per parameter by study phase will be presented including also the number of participants per abnormality. A tabulation of percentage and number of the participants who have treatment-emergent worst abnormalities per parameter (i.e. for HR, PR, QRS, and QTcF) and analysis phase will also be presented.

A cross-tabulation of the worst change from baseline abnormalities (i.e. for QTcF) versus the baseline category per parameter will be presented by intervention arm and study phase.

Frequency tabulations of categorized corrected QT/QTc change from baseline (≤ 30 msec, $> 30 - \leq 60$ msec, > 60 msec) and categorized corrected QT/QTc interval values (≤ 450 msec, $> 450 - \leq 480$ msec, $> 480 - \leq 500$ msec, > 500 msec) per timepoint will be presented by intervention arm.

Listings including all parameters for participants with at least one treatment-emergent abnormality (on actual values or change from baseline), including all findings (e.g. interpretation, rhythm, or technical findings) for participants with uncorrected QT values ≥ 500 ms will be provided separately.

6.4. Vital Signs and Body Temperature

6.4.1. Definitions

The following parameters measurements will be analyzed:

- Supine pulse rate (bpm)
- Supine systolic blood pressure (mmHg)
- Supine diastolic blood pressure (mmHg)
- Body temperature (°C)

The abnormalities in vital signs will be determined according to the criteria specified in the Cardiovascular Safety – Abnormalities Table (see Clinical Protocol Section 10.7, Appendix 7).

An assessment is treatment-emergent if abnormality worsened as compared to the abnormality at baseline; this also includes the shift from abnormally high to abnormally low and vice-versa. Post-baseline abnormalities are always treatment-emergent with regard to missing abnormalities at baseline. The abnormally high values (i.e. abnormally high, grade 1 or mild, grade 2 or moderate, grade 3 or severe) versus the abnormally low values are considered equally important.

For each parameter, a “worst-case” analysis will be performed by using the worst abnormality and time point per participant. Worst-case will be derived within each phase, including unscheduled assessments. In case the same subject has both abnormalities (low and high) for the same test within the same phase, the participant will be counted in the analysis for both abnormality directions (abnormally high and low).

Change from baseline is defined as follows: value at a given time point minus baseline value.

6.4.2. Analysis Methods

Vital signs records with partial dates (any of day/month/year is missing) will not be used in the analysis but will be listed.

Descriptive statistics of continuous vital sign parameters and body temperature will be calculated for observed values and changes from baseline at each scheduled time point.

Shift tables will be provided summarizing the shift in vital sign and body temperature values from baseline over time with respect to abnormality criteria (low, normal, high) for each parameter by study phase.

A cross-tabulation of the worst abnormalities versus baseline per parameter and study phase will be presented including also the number of participants per abnormality, the number of participants with treatment emergent abnormalities per abnormality.

A tabulation of percentage and number of the participants who have treatment-emergent worst abnormalities per parameter and study phase will be included.

A listing including all parameters for participants with at least one treatment-emergent abnormality (on actual values or change from baseline) is provided. Additional vital signs assessments corresponding to the rash eCRF pages will be only listed as applicable.

6.5. Physical Examination

The physical examination findings and abnormalities will be listed.

7. VIRAL GENOME SEQUENCE ANALYSIS

The sequencing of samples from participants in this study may be triggered by the sponsor virologist based on changes in HBV DNA levels observed in each individual subject and the limits of the sequencing assay.

Viral genome sequence analysis will be performed to evaluate the presence of genetic variations (including substitutions) associated with JNJ-56136379, JNJ-3989, and/or ETV or TDF/TAF treatment on both nucleotide and/or amino acid level.

Sequencing of the HBV genome will be performed to monitor HBV variants present at the time points indicated in Section 7.1.

Virology results will be presented by specified timepoints and genetic region and position of interest. A separate virology report will be prepared.

7.1. Time Points and Samples

When analyzing sequencing data, the focus will be on genetic variants at

- Time Point of Sequence at Virologic Breakthrough: time point with sequence data available closest to the time point of virologic breakthrough (FTPT) (see Section 5.3.1.1.7 for virologic breakthrough definition)
- Time Point of Sequence at Virologic Flare: time point with sequence data available closest to the time point of Virologic flare (see Section 5.3.1.1.6 for virologic flare definition)
- Time Point of Sequence at Re-treatment during Post-treatment Follow-up: time point with sequence data available closest to time point where re-treatment criteria is met (see Section 5.3.1.1.8)
- Aggregated Post-Baseline Study Period (ASSEQ): entire post-baseline study period, aggregate of all available time points in the study with sequence data available
- Aggregated Post-Baseline Treatment Period (ATSEQ): entire post-baseline treatment period, aggregate of all available post-baseline time points during the treatment phase with sequence data available

Given only participants who are on stable NA treatment and who have HBV DNA <60 IU/mL at screening will be enrolled in this study, no baseline sequencing can be performed. In the exceptional case baseline HBV DNA levels are above the sensitivity limit of the sequencing assay used, the baseline sample may be sequenced.

7.2. Definitions

- The presence of genetic variations is defined as changes (on the amino acid or nucleotide level) in the subject viral sequence compared to a HBV genotype specific reference viral sequence and/or the universal HBV reference sequence (NCBI ID X02763). The reference sequence to be used is provided in the database. The reference viral sequences to be used are:

Virus	Genotype	NCBI genbank accession	NGS isolate name	Sanger genbank accession	Sanger isolate name
HBV	A	X02763	adw2	X02763	adw2
HBV	B	AB219428	PNN3	D00329	pJDW233
HBV	C	GQ924620	M38	AB014362	03D03HCC
HBV	D	AF121240	11066	V01460	ayw
HBV	E	AB106564	GA325	X75657	ayw4
HBV	F	AY090458	70H	X75658	adw4q
HBV	G	AF160501	IG29227	AB064311	USG825
HBV	H	FJ356716	CL150171	AY090460	LAS2523
HBV	I	EU833891	H4536-07		

- Wild type: If at certain position the amino acid/nucleotide in the subject sequence matches the reference sequence, that is no genetic variation is present at that position, the virus is considered to be wild type at that position.

7.3. Parameters to Analyze

At specified time points and for each list specified in the section below, the following parameters will be analyzed:

- Number (%) of subjects with a substitution at a specific position.
- Number (%) of subjects with a specific substitution.
- Number (%) of subjects with a specific substitution profile
- Number (%) of subjects with substitutions on amino acid level (overall and by HBV genotype (A, B, C, D, E, F, G, H, I and Unknown))
 - in the HBV core protein,
 - at HBV core protein positions of interest,
 - at positions of interest in the RT-domain of the polymerase,
 - at positions of interest in the major hydrophilic loop of HBsAg.
- Number (%) of subjects with substitutions on nucleotide level
 - at the binding site positions of JNJ-3989 (i.e. JNJ-3976 and JNJ-3924) (overall and by HBV genotype (A, B, C, D, E, F, G, H, I and Unknown)).
 - in the precore (genome position 1896) and basal core promotor (genome positions 1762/1764) region (overall, by HBV genotype (A, B, C, D, E, F, G, H, I and Unknown))

The focus will be on substitutions at a time point, and reversion to wild type state. The above summaries will be repeated for genetic variations (not needed for CSR).

In the sequence analysis, sequences will be mapped to the respective genotype specific reference sequences after which nt changes and aa substitutions will be annotated compared to the respective genotype specific reference (see Table in Section 7.2). In addition, the X02763 (HBV genotype

A), which is the master reference sequence of the HBV db, will be used as universal reference sequence.

All NGS data will be collected using a nt and aa read frequency cut-off of ≥ 0.01 . For the analysis of nt changes and/or aa substitutions in terms of frequency of variant, a read frequency cut-off of ≥ 0.15 will be used. The persistence of nt changes and aa substitutions will be evaluated using a cut-off of ≥ 0.15 and ≥ 0.01 .

The applicability of the sequencing approach described here (eg, the 0.01 sensitivity limit) will be assessed during the development program and might be adapted if needed.

7.4. Positions & Genetic Variations of Interest

On the nucleotide level:

In the basal core promotor region:

- 1762 and 1764 (ECo numbering will be used)

In the precore region:

- 1896 (ECo numbering will be used)

In the basal core/precure region

- Combination of basal core promotor and/or precore region

In the JNJ-3989 binding pocket positions:

- JNJ-3976 (S Trigger)

- Long list (N=21): 259, 260, 261, 262, 263, 264, 265, 266, 267, 268, 269, 270, 271, 272, 273, 274, 275, 276, 277, 278, and 279
- Short list (N=17): 262, 263, 264, 265, 266, 267, 268, 269, 270, 271, 272, 273, 274, 275, 276, 277, and 278

- JNJ-3924 (X Trigger)

- Long list (N=21): 1779, 1780, 1781, 1782, 1783, 1784, 1785, 1786, 1787, 1788, 1789, 1790, 1791, 1792, 1793, 1794, 1795, 1796, 1797, 1798, and 1799
- Short list (N=17): 1782, 1783, 1784, 1785, 1786, 1787, 1788, 1789, 1790, 1791, 1792, 1793, 1794, 1795, 1796, 1797, and 1798

- In the JNJ-3976/JNJ-3924

Combination of JNJ-3989 binding site positions JNJ-3976 and/or JNJ-3924

Amino acid level:

In the HBV core protein (based on putative binding pocket [[Bourne C. et al., 2006 & Katen S.P. et al., 2013](#)])

- Long list (n=48): 18, 19, 23, 24, 25, 26, 27, 28, 29, 30, 31, 32, 33, 37, 38, 102, 103, 105, 106, 107, 109, 110, 111, 114, 115, 116, 117, 118, 119, 121, 122, 123, 124, 125, 126, 127, 128, 129, 131, 132, 133, 134, 136, 137, 138, 139, 140, 141
- Due to an insertion of 12 amino acids in the N-terminal part of core, the 48 HBV Core Protein positions of interest for HBV genotype G are 30, 31, 35, 36, 37, 38, 39, 40, 41, 42, 43, 44, 45, 49, 50, 114, 115, 117, 118, 119, 121, 122, 123, 126, 127, 128, 129, 130, 131, 133, 134, 135, 136, 137, 138, 139, 140, 141, 143, 144, 146, 148, 149, 150, 151, 152, 153.

Based on some recent more detailed published structural data ([Klumpp K. et al., 2015](#), [Qiu Z. et al., 2016](#), [Zhou Z. et al., 2017](#), & [Tu J. et al., 2017](#)), and some in house structural analysis, a more shortened list of core positions of interest can be defined:

- Short list (n=29): 23, 24, 25, 29, 30, 33, 37, 38, 102, 105, 106, 109, 110, 118, 121, 122, 124, 125, 127, 128, 129, 132, 133, 134, 137, 138, 139, 140, 141
 - Due to an insertion of 12 amino acids in the N-terminal part of core, the 29 HBV Core Protein positions of interest for HBV genotype G are 35, 36, 37, 41, 42, 45, 49, 50, 114, 117, 118, 121, 122, 130, 133, 134, 136, 137, 139, 140, 141, 144, 145, 146, 149, 150, 151, 152, 153
- Short list (n=15): 23, 24, 25, 29, 30, 33, 37, 105, 106, 109, 110, 118, 124, 127, 128.
 - Due to an insertion of 12 amino acids in the N-terminal part of core, the 15 HBV Core Protein positions of interest for HBV genotype G are 35, 36, 37, 41, 42, 45, 49, 117, 118, 121, 122, 130, 136, 139, 140

In the pol/RT protein:

- 169, 173, 180, 181, 184, 194, 202, 204, 236, 250

See below breakdown of relative amino acid position of the 10 POI in the RT-domain of polymerase by HBV genotype.

HBV GT-A		HBV-GT-B/C/F/H/I		HBV GT-D		HBV-GT-E/G	
POL number	RT number	POL number	RT number	POL number	RT number	POL number	RT number
517	169	515	169	504	169	514	169
521	173	519	173	508	173	518	173
528	180	526	180	515	180	525	180
529	181	527	181	516	181	526	181
532	184	530	184	519	184	529	184
542	194	540	194	529	194	539	194
550	202	548	202	537	202	547	202
552	204	550	204	539	204	549	204
584	236	582	236	571	236	581	236
598	250	596	250	585	250	595	250

In the major hydrophilic loop of the S-protein region (linked to vaccine escape):

- Amino acids 99 to 169
- Positions of interest: 116, 118, 120, 126, 129, 130, 131, 133, 134, 141, 142, 143, 144, 145, 164, 195, and 196.

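### SAP 7.4 announces 48 core-protein positions for genotype G but prints 47: position 145 is missing from the long list, although the 29-position short list has it

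*SAP*

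**What the plan says.** SAP 7.4 sets out three nested sets of HBV core positions of interest, of 48, 29 and 15 residues, and repeats each in genotype G numbering. The longest begins "Long list (n=48): 18, 19, 23, 24, 25, 26, 27, 28, 29, 30" and ends "126, 127, 128, 129, 131, 132, 133, 134, 136, 137, 138, 139, 140, 141". The reason given for the separate genotype G numbering is the same each time: "Due to an insertion of 12 amino acids in the N-terminal part of core".

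For the long list the SAP then announces "the 48 HBV Core Protein positions of interest for HBV genotype G are", and the printed numbers end "140, 141, 143, 144, 146, 148, 149, 150, 151, 152, 153". For the 29-position list it announces "the 29 HBV Core Protein positions of interest for HBV genotype G are", and those numbers end "139, 140, 141, 144, 145, 146, 149, 150, 151, 152, 153".

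SAP 7.3 makes these lists operative. The sequence parameters are analysed for every list in 7.4, and the amino-acid counts at core positions of interest are reported overall and by HBV genotype, with G named.

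Further down in 7.4, the heading for the major hydrophilic loop of the S-protein carries two bullets. One is the range "Amino acids 99 to 169". The other is a list of 17 positions of interest whose last two entries are 195 and 196.

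**The concern.** The stated count and the printed list disagree, and the two genotype G lists disagree with each other. In the parent numbering every short-list position is also on the long list. In genotype G numbering that nesting fails at 145.

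A programmer working from the printed text would build a 47-position genotype G filter. A genotype G participant whose only substitution in the pocket is at 145 would then be positive on the 29-position summary and negative on the 48-position summary. That cannot happen if the lists are nested as intended. The long-list count would be one too low for each such participant, both in the genotype G row and in the overall row.

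The loop entry raises a smaller question of the same kind: two of the positions filed under the loop heading fall outside the range printed beside it.

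**Working it through.** **Inputs.** All come from SAP 7.4: the parent long list (stated 48), the genotype G long list (stated 48), the 29- and 15-position lists with their genotype G versions, and the loop range and loop list. The mapping rule is genotype G position = parent position + 12.

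**Long list, block by block.**

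| Parent block | Count | Expected for G (+12) | Printed for G | Count |
|---|---|---|---|---|
| 18, 19 | 2 | 30, 31 | 30, 31 | 2 |
| 23 to 33 | 11 | 35 to 45 | 35 to 45 | 11 |
| 37, 38 | 2 | 49, 50 | 49, 50 | 2 |
| 102, 103 | 2 | 114, 115 | 114, 115 | 2 |
| 105 to 107 | 3 | 117 to 119 | 117 to 119 | 3 |
| 109 to 111 | 3 | 121 to 123 | 121 to 123 | 3 |
| 114 to 119 | 6 | 126 to 131 | 126 to 131 | 6 |
| 121 to 129 | 9 | 133 to 141 | 133 to 141 | 9 |
| 131 to 134 | 4 | 143 to 146 | 143, 144, 146 | 3 |
| 136 to 141 | 6 | 148 to 153 | 148 to 153 | 6 |

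Parent total: 2 + 11 + 2 + 2 + 3 + 3 + 6 + 9 + 4 + 6 = 48, as stated.

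Genotype G total: 2 + 11 + 2 + 2 + 3 + 3 + 6 + 9 + 3 + 6 = 47, against 48 stated.

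The only missing number is 145 = 133 + 12, and there are no extra numbers.

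**Shorter lists.** The 29-position list and its genotype G version have 29 entries each and match exactly under the +12 rule. The 15-position pair has 15 and 15 and also matches exactly. The only genotype G short-list position absent from the genotype G long list is 145.

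**After correction.** With 145 added, the genotype G long list has 47 + 1 = 48 entries, equals the shifted parent list, and contains the whole 29-position list.

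**Controls elsewhere in 7.4.** The S-trigger and X-trigger lists have 21 and 17 positions each, as stated. In the polymerase table the difference between the POL and RT numbers is constant within each genotype column (348, 346, 335 and 345). The missing 145 is an isolated slip.

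**Loop list.** Of the 17 positions, 15 (116 to 164) lie within 99 to 169 and two (195 and 196) lie above it.

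**The case against.** The best case against acting on 145 is that the error corrects itself and hardly matters. The intended value is plain from the stated count, the insertion rule, the parent list and the short list, so a routine programming check should catch it. Even if the list is programmed as printed, a substitution at 145 still appears in the whole-core count in SAP 7.3, in the 29-position summary and in the participant listings in SAP 7.5. SAP 7.3 also compares sequences with a universal genotype A reference. If positions were numbered on that reference, which the SAP does not spell out, the residue would be 133, which is listed. Sequencing depends on the virologist's request and on HBV DNA level, and SAP 7.5 produces a frequency output only when at least 5 participants have the relevant sequence data, so a genotype G table may never be made. All of this stands and limits the size of the point. It does not make the printed list right, and the threshold of 5 does not remove a genotype G participant from an overall count.

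Two stronger readings are tempting.

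- A reader might infer that substitutions at 195 and 196 will be miscounted. The documents do not support this. SAP 7.3 counts substitutions at the listed positions, both are listed, and neither 7.3 nor 7.5 calls for a filter by 99 to 169. What remains is a label that does not fit two entries.
- A reader might infer that the virology tables will contradict each other. They would do so only if a genotype G participant has a substitution at exactly 145 and at no other long-list position, and nothing in the documents shows that one will.

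**Conclusion.** The omission is real: SAP 7.4 states 48 genotype G core positions and prints 47, and three separate statements in the same section (the count, the insertion rule and the short list) identify 145 as the missing one. The gap sits in running text, not in a table, so a fault in reading the PDF is unlikely, but the source file should be checked.

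The size is 1 position in 48, for genotype G participants only. The documents give no expected number of them, and it may be zero. The direction is an undercount in the long-list summaries, on the assumption that the list is programmed as printed in genotype G numbering. These outputs are descriptive and serve the exploratory objective on intervention-associated mutations. The primary endpoint, its estimand, the sample size, the power and the type I error are untouched.

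The 195 and 196 entries are a labelling mismatch affecting 2 of 17 positions. The heading, the range or the list could be the loose element, and the documents do not say which. This is a minor point, worth correcting because the list is a programming specification and the correction is nearly free.

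**What to change.** Insert 145 between 144 and 146 in the genotype G version of the 48-position list in SAP 7.4, and check any program already written from that list.

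Ask the sponsor's virologist to reconcile the loop heading, the 99 to 169 range and the 17 listed positions, and to amend whichever is wrong so that the output title describes what is counted.

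The cost is one number added to a list and one clarification. SAP Amendment 1 already revised Section 7.4 at Virology's request, so a further edit there is routine. No data collection or other analysis changes.
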